9.2 Patient demographics and other baseline characteristics

Descriptive statistics (mean, median, standard deviation, minimum, and maximum for continuous variables and number and percentage for categorical variables) for the

demographic and other baseline characteristics variables will be provided for the 2 randomized Core treatment groups. In addition, the baseline comparability between these two treatment groups will be evaluated for key demographic and other baseline characteristics variables for Group 1. Categorical variables will be evaluated using Fisher's exact test, and the continuous variables will be evaluated using a one-way analysis of variance (ANOVA).

Note that these tests of comparability are performed for descriptive purpose only, and will not be considered to define any formal basis for determining factors which should be included in statistical analysis models. However, when these tests yield significant results they can be used as extra information in interpreting any treatment-by-factor interactions that are observed in the sensitivity analyses performed on the key secondary efficacy variables.

All analyses will be performed based on the FAS-1 for Group 1.

Similar descriptive statistics for single treatment arm will be reported on FAS-2 for Group 2 also.

The relevant medical history/current medical conditions for the Extension study include relevant medical history/current medical conditions recorded in the Core study and adverse events occurring during the Core study or after the end of Core study but before the first study drug infusion in the Extension study for Group 1. The number and percentage of patients with relevant medical history/current medical conditions for the Extension study will be presented for each core treatment by primary system organ class and preferred term of the MedDRA dictionary. The number and percentages of adverse events that started before the Extension study and is still present at the first drug infusion in the Extension study will be presented for each core treatment by primary system organ class and preferred term. Similar medical history/current medical conditions except adverse events will also be recorded for Group 2. The number and percentage of patients with relevant medical history/current medical conditions for the Extension study will be presented for single treatment arm by primary system organ class and preferred term of the MedDRA dictionary.

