Summary statistics (means, medians, standard deviations, ranges) of raw data and change from baseline values) will be presented. In addition, shift tables using extended normal ranges (baseline to post-baseline value) will be provided in order to compare a patient's baseline laboratory evaluation relative to each study visit. For the shift tables, the normal laboratory values will be used to evaluate whether a particular laboratory test value is normal, low, or high for each visit value relative to whether or not the baseline value is normal, low, or high. These summaries will be presented by laboratory test and by the core treatment group. For Group 1, both changes from Baseline 1 (first visit of the Core) and Baseline 2 (first visit of the Extension) will be reported. The number and percentage of patients who have lab values that meet the criteria for being clinically notable after the first dose of study medication will be presented by the Core treatment group. Patient listings that present each patient's lab profile for those tests that are outside of the clinically notable ranges will also be provided.

The ranges of the normal laboratory values as well as the alert values for the safety monitoring will be provided in the Laboratory Manual, which will be attached to the protocol as an exhibit.

Data from other assessments (e.g. vital signs) will be listed, notable values will be flagged, and any other information collected will be listed as appropriate. The number and percentage of patients who have vital sign values that meet the criteria for being clinically notable after the first dose of study medication will be presented by the Core treatment group. Any statistical tests performed to explore the data will be used only to highlight any interesting comparisons that may warrant further consideration.

No statistical test will be performed for Group 2.

Details will be available in statistical analysis plan.

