9.5 Analysis of secondary variables

9.5.1 Efficacy variables

If otherwise not specified, the efficacy data for Group 1 will be summarized and analyzed with respect to Baseline 1 (first visit of the Core) and Baseline 2 (first visit of the Extension) will be presented by the Core treatment group and visit. However only summary statistics will be presented with respect to Baseline 2 and will be presented only for the single treatment. Data will be presented in summary tables, graphs, and listings to give an overview of the long-term efficacy maintenance. The mean, median, standard deviations, and range of each variable and its change from baseline measured on a continuous scale, will be presented by treatment group and visit. Frequency tables will be provided for categorical variables by treatment group and visit. All hypothesis tests (only for Group 1) will be evaluated at a 0.05 level of significance, and the p-values will be rounded to the 4th decimal place. Change from baseline at Month 18/24 is defined as value at Month 18/24 – value at baseline. Percentage change baseline is defined as 100 times the change from baseline divided by the baseline value. Missing values will not be imputed or replaced.

All efficacy analysis will be performed using FAS-1 and FAS-2 separately.

Data from all centers will be combined so that an adequate number of patients are available for analysis. Small centers will be pooled using an algorithm specified before database lock.

9.5.1.1 Change in lumbar spine areal BMD Z-score at Months 18 and 24 relative to baseline

Group 1: the percentage change in LS-BMD Z-score at Months 18 and 24 relative to both baselines between zoledronic acid and placebo (the Core treatment groups) will be evaluated using an ANCOVA model with treatment, pooled center, underlying condition treated with GCs and baseline LS-BMD Z-score as explanatory variables. The 2-sided 95% confidence intervals for the difference in least squares means between zoledronic acid and placebo will be provided.

Group 2: percentage changes in LS-BMD Z-score at Months 18 and 24 relative to Baseline 2 (Visit 8A/9) for zoledronic acid will be evaluated.

9.5.1.2 Change in lumbar spine and total body BMC at Months 18 and 24 relative to baseline

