### **Demographic and other baseline characteristics**

[figure not shown]
Demographic variables and baseline characteristics will be summarized at both core and extension baselines.

Baseline demographic information for continuing patients was collected at the beginning of the Core study and will not be collected again in the extension study.

Descriptive statistics for the following demographic variables and baseline characteristics will be summarized for core period by core treatment group using FAS. Similar summaries will be performed for extension period but sex, race, ethnicity and non-vertebral fractures will be excluded. Vertebral morphometry will be removed as well because it is no longer an endpoint in the extension period.

Age at extension enrollment (years)

- Age group at extension enrollment ( $\geq 6$  years to  $\leq 9$  years;  $\geq 10$  years to  $\leq 19$  years)
- Sex
- Race
- Ethnicity

- 
- Weight (kg)
  - BMI ( $\text{kg}/\text{m}^2$ ). The baseline standing height will be used in BMI calculation.
  - Tanner evaluation (breast development, genital stage, pubic hair, and whether menarche has occurred)
  - Lumbar spine BMD Z-score
  - Lumbar spine BMD Z-score category
    - $\leq -2.0$
    - $> -2.0$  to  $\leq -1.0$

- $> -1.0$  to  $\leq -0.5$
- Lumbar spine Bone Mineral Content (BMC) (g)
- Total body BMC (g)
- Serum 25-hydroxy vitamin D (nmol/L)
- Serum calcium level (mmol/L)
- Serum NTX (nmol BCE/L)
- Serum TRAP-5b (U/L)
- Serum BSAP (ng/mL)
- Serum P1NP (ng/mL)
- Vertebral morphometry
- Non-vertebral fractures
- Metacarpal cortical width (mm)

- Pain score

In addition, the core baseline comparability between core treatment groups will be evaluated for demographic and other baseline characteristics variables. Categorical variables will be evaluated using Fisher's exact test, and the continuous variables will be evaluated using a Wilcoxon rank-sum test.

Note that these tests of comparability are performed for descriptive purpose only, and will not be considered to define any formal basis for determining factors which should be included in statistical analysis models. However, when these tests yield significant results they can be used as extra information in interpreting any treatment-by-factor interactions that are observed in the sensitivity analyses performed on the primary and secondary efficacy variables.

All demographic and baseline characteristic data will be listed as presented above.

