## Analysis for efficacy variables

If otherwise not specified, the efficacy data will be summarized and analyzed with respect to core baseline only and will be presented by the core treatment group and visit. The mean, median, standard deviations, and range of each variable and its change from baseline measured on a continuous scale, will be presented by core treatment group and visit. Number and percentage of patients will be presented for categorical variables by core treatment group and visit. All hypothesis tests will be evaluated at a 0.05 level of significance, and the p-values will be rounded to the 4th decimal place. Change from baseline at Month X is defined as value at Month X - value at baseline. Percentage change from baseline is defined as 100 times the change from baseline divided by the baseline value. Missing values will not be imputed or replaced.

The efficacy variables and their analysis methods are described below.

- **Percent change in lumbar spine areal BMD Z-score at Months 18 and 24 relative to baseline, zoledronic acid group vs. placebo**

The percent change in LS-BMD Z-score at Months 18 and 24 relative to core baseline between zoledronic acid and placebo (the core treatment groups) will be evaluated using an ANCOVA model with core treatment, pooled center, underlying condition treated with glucocorticoids and core baseline LS-BMD Z-score as explanatory variables and pooled centers as random effect.

From the model, core treatment difference in least squares means between zoledronic acid group vs. placebo group will be estimated and presented together with two-sided 95% CI and p-value. In the same table, the LS means and standard errors for percent change from baseline in LS-BMD Z-score at Month 18 and Month 24 will be presented for each core treatment group. Descriptive statistics will also be shown for baseline, Month 18 and Month 24 visits.

- **Change in lumbar spine and total body BMC at Months 18 and 24 relative to baseline, zoledronic acid group vs. placebo**

The change in BMC at the lumbar spine and total body at Months 18 and 24 relative to core baseline between zoledronic acid and placebo will be evaluated using an ANCOVA model with core treatment, pooled center, underlying condition treated with glucocorticoids and core baseline BMC as explanatory variables and pooled centers as random effect.

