The reduction in pain from core baseline by visit will be evaluated based on whether or not patients have a decrease in their FPS-R from baseline. If pain remains the same or worsens from baseline a patient will be classified as ‘0’ and if the pain scale decreased then the patient will be classified as ‘1’. Whether or not a patient experiences a decrease in pain will be evaluated using a logistic regression model with core treatment, pooled centers, underlying condition treated with glucocorticoids and baseline pain score as explanatory variables.

Regression analysis will be carried out with respect to both baselines (core baseline as well as extension baseline).

[figure not shown]

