### **Other analyses**

The following core data for the patients in the extension FAS will be summarized and analyzed similarly at core visits to give an overall profile during the 24 months core and extension combined period:

- Change in LS-BMD Z-score relative to baseline
- Change in lumbar spine and total body BMC relative to baseline
- Relative change in biochemical markers of bone turnover (Serum NTX, TRAP-5b, BSAP and PINP)
- Change in 2nd metacarpal cortical width relative to baseline

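### At least 26 secondary comparisons of the Core treatment groups are each judged at 0.05, with no key contrast, testing order or exploratory label

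*SAP*

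**What the plan says.** The primary objective in both documents is safety in Group 1, and every efficacy endpoint is secondary.

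- **Level.** The SAP, under Analysis for efficacy variables, states: "All hypothesis tests will be evaluated at a 0.05 level of significance". Protocol 9.5.1 states: "All hypothesis tests (only for Group 1) will be evaluated at a 0.05 level of significance".
- **Output.** For each ANCOVA endpoint the SAP says that the difference between Core groups "will be estimated and presented together with two-sided 95% CI and p-value". Fractures are compared by Fisher's exact test and pain reduction by logistic regression.
- **Repeats.** For pain, "Regression analysis will be carried out with respect to both baselines". Metacarpal cortical width is also analysed from both baselines. Under Other analyses, Core-period data for several endpoints "will be summarized and analyzed similarly at core visits".
- **Exploratory or descriptive labels.** These appear elsewhere. Baseline comparability tests are called descriptive (protocol 9.2; SAP, Demographic and other baseline characteristics). Protocol 9.4.1, on safety, says: "Any statistical tests performed to explore the data will be used only to highlight any interesting comparisons that may warrant further consideration". The general descriptive statement (protocol 9.4.2; SAP, Statistical model, hypothesis, and method of analysis) belongs to the primary safety analysis. None of these labels reaches the efficacy tests.
- **Undefined terms.** Protocol 9.2 refers to "sensitivity analyses performed on the key secondary efficacy variables" and the SAP to "sensitivity analyses performed on the primary and secondary efficacy variables". Neither document says which variables are key, and neither has a primary efficacy variable.

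**The concern.** The plan pairs a significance rule with a long list of comparisons and does not rank them. An isolated p<0.05 for pain at Month 21 from one of two baselines would have the same standing as the result for lumbar spine BMD Z-score at Month 24. The endpoints may well disagree across markers, BMC, fractures and pain, and nothing fixed in advance says which comparison carries the efficacy message.

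This matters although efficacy is secondary. The study title includes efficacy, and protocol 1.2 says the study should help show whether a second year of treatment adds benefit. Readers will therefore look at these p-values. The exposure is to selective emphasis in the report, not to a wrong decision on the primary objective.

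**Working it through.** The documents state no family-wise error rate, power or effect size, so there is no figure of theirs to reproduce. The only stated input is 0.05 per test. The ANCOVA confidence intervals are two-sided, and two-sided tests are assumed throughout.

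**Step 1: count the tests** (SAP, Analysis for efficacy variables)

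| Endpoint | Structure | Tests |
|---|---|---|
| Lumbar spine BMD Z-score | Months 18, 24 | 2 |
| BMC | 2 sites × 2 visits | 4 |
| Bone markers | 4 markers × 2 visits | 8 |
| Vertebral fractures | new; new morphometric | 2 |
| Metacarpal cortical width | Month 24 × 2 baselines | 2 |
| Pain reduction | Months 15, 18, 21, 24 × 2 baselines | 8 |

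Total: 2 + 4 + 8 + 2 + 2 + 8 = **26**.

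Other readings change the count:
- Core baseline only: 2 + 4 + 8 + 2 + 1 + 4 = 21.
- Pain at Visit 9 also tested against Core baseline: 27.
- Both baselines for every ANCOVA, as protocol 9.5.1 reads: the 2 + 4 + 8 = 14 tests done from one baseline are doubled, giving 26 + 14 = 40.
- The Core-visit analyses add more. Their number is left open because the Core visit schedule is not in these documents.

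**Step 2: chance of at least one p<0.05 with no true difference on any endpoint**

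Independent tests: 1 − 0.95^26 = 0.736. Expected number of false positives, whatever the correlation: 26 × 0.05 = 1.3.

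Common correlation ρ between the test statistics, with φ and Φ the standard normal density and distribution function:

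1 − ∫ φ(t) [Φ((1.96 − √ρ·t)/√(1−ρ)) − Φ((−1.96 − √ρ·t)/√(1−ρ))]^k dt

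| ρ (assumed) | k = 21 | k = 26 | k = 40 |
|---|---|---|---|
| 0 | 65.9% | 73.6% | 87.1% |
| 0.3 | 55.5% | 61.9% | 74.5% |
| 0.5 | 42.9% | 47.5% | 57.1% |
| 0.8 | 22.8% | 24.5% | 28.0% |
| 0.9 | 15.7% | 16.6% | 18.4% |

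**Step 3: a less uniform correlation pattern**

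The 26 tests were simulated (400,000 draws per scenario) with assumed correlations of 0.5 to 0.9 within an endpoint, 0.3 to 0.7 between related endpoints and 0 to 0.3 across unrelated ones. The chance was 42% to 66%. Fisher's test is conservative with few events. If the two fracture tests never reject, the range is 39% to 63%.

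**Step 4: the two treatment of tests, side by side**

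Where the authors wanted tests read as descriptive or exploratory (baseline comparability, safety), they said so. The efficacy section has a significance rule instead, so a descriptive intent cannot be read into it.

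**The case against.** Several points on the other side are sound.

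- **The rate depends on unstated correlations.** A reader might infer that a false significant result is likely, at about 47%. That figure holds only if all 26 statistics share a correlation of 0.5, which neither document states, and a figure below one half is not likely in the ordinary sense. Only the range can be supported.
- **No family-wise promise is broken.** A reader might set the family-wise rate against 0.05 and say the plan exceeds its stated error. The documents state a per-test level only, so the two are different quantities.
- **The global null is a reference case.** Most tests measure change from Core baseline between arms that had zoledronic acid or placebo in year 1, and protocol 3.3 expects superiority over placebo on Z-score in the Core study. True differences in BMD, BMC and markers are plausible, so 1.3 is not a forecast.
- **The contrast is not drug against placebo.** The SAP's endpoint titles invite that reading. All extension patients receive zoledronic acid (protocol 3.1, 3.4, 5.2), so the comparison is of earlier with delayed treatment. Error control would not change that.
- **The stakes are limited.** Size follows from Core rollover without a power claim, the Group 1 efficacy objectives are to evaluate rather than to demonstrate, and the SAP already produces estimates with 95% CIs for the ANCOVA endpoints and for the pain odds ratio.

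All of this narrows the size and importance of the point. It does not supply the missing label or ranking, whose absence depends on no assumed correlation.

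**Conclusion.** The point holds as a wording defect with real consequences for what may be concluded. At least 26 secondary comparisons carry a 0.05 significance rule without a key contrast, order or exploratory label in the visible text. On the reference assumption of no true difference anywhere, the chance of at least one nominally significant result is about 17% to 74% for 26 tests, depending on correlation. The between-group correlations and the global null are assumptions, not facts from the documents. The primary safety objective is untouched, and the change is worth making mainly because it is cheap. The undefined primary and key secondary efficacy terms are a separate editorial matter and add little to the case.

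**What to change.** Replace the significance sentence in the SAP (Analysis for efficacy variables) and in protocol 9.5.1 with:

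> Efficacy comparisons between Core treatment groups are exploratory. Estimates and 95% CIs are the main presentation. P-values are nominal, not adjusted for multiplicity, and will not be used to declare statistical significance.

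If the sponsor wants one formal test at two-sided 0.05, it should name one endpoint, visit and baseline before database lock and leave all other efficacy p-values nominal. The choice is the sponsor's. If lumbar spine BMD Z-score is chosen, the test should use absolute change, as the secondary objective is worded, and not the percent change in the SAP's analysis. With baselines of −0.5 or worse, percent change reverses sign and depends heavily on the starting value. For illustration, a gain of 0.5 is 100 × 0.5/(−0.5) = −100% from a baseline of −0.5, but 100 × 0.5/(−2.0) = −25% from −2.0.

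As a separate clean-up, delete or define the primary and key secondary efficacy terms in the SAP's baseline section and protocol 9.2.

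Cost: a few sentences and table footnotes, with no new data or analyses. The downside is that secondary efficacy results, apart from any single named test, can no longer be reported as statistically significant.

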2.2 Secondary objective(s)

[figure not shown]
Group 1 secondary objectives:

1. To evaluate the change from baseline 1 (Visit 1 of the Core study) in LS-BMD Z-score at Month 18 and 24 by core treatment group.
2. To evaluate the change from baseline 1 (Visit 1 of the Core study) in LS and total body BMC at Month 18 and 24 by core treatment group.
3. To evaluate the change from baseline 1 (Visit 1 of the Core study) in serum N-terminal propeptide type I collagen (P1NP), cross linked N-telopeptide (NTX), bone specific alkaline phosphatase (BSAP) and tartrate-resistant acid phosphatase isoform 5b (TRAP-5b) at Month 18 and 24 by core treatment group.
4. To evaluate the proportion of patients with new clinical vertebral fractures during the 12 month extension period by core treatment group.
5. To evaluate the proportion of patients with new morphometric vertebral fracture during the 12 month extension period by core treatment group.
6. To evaluate the change from baseline 1 (Visit 1 of the Core study) in pain using the Faces Pain Scale-Revised (FPS-R) at Month 15, 18, 21 and 24 by core treatment group.
7. To evaluate the change from baseline 1 (Visit 1 of the Core study) in 2nd metacarpal cortical width at month 24 by core treatment group.
8. To evaluate the change from baseline 1 (Visit 1 of the Core study) in bone age and 2nd metacarpal cortical width at month 24 by core treatment group.

Group 2 secondary objectives:

1. To evaluate the change from (Extension) baseline 2 (visit 8A) in LS- BMD Z-score at Month 6 and 12.
2. To evaluate the change from (Extension) baseline 2 (visit 8A) in LS and total body BMC at Month 6 and 12.

3. To evaluate the relative change from (Extension) baseline 2 in serum N-terminal propeptide type I collagen (P1NP), cross linked N-telopeptide (NTX), bone specific alkaline phosphatase (BSAP) and tartrate-resistant acid phosphatase isoform 5b (TRAP-5b) at Month 6 and 12.
4. To evaluate the proportion of patients with new clinical vertebral fractures during the 12 month period.
5. To evaluate the proportion of patients with new morphometric vertebral fracture during the 12 month period.
6. To evaluate the change from (Extension) baseline 2 in pain using the Faces Pain Scale-Revised (FPS-R) at Month 3, 6, 9 and 12.
7. To evaluate the change from (Extension) baseline 2 in bone age and 2nd metacarpal cortical width at Month 12.

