3.1 Study design

This study is a 1-year open-label extension to the CZOL446H2337 Core study. The study uses a single treatment arm (zoledronic acid); there will be no placebo or active control group. All patients will be osteoporotic children and adolescents receiving GC therapy of any duration within the 12 months preceding Baseline (Visit 1 of the Core study for Group 1; Visit 8A of this study for Group 2). All patients must manifest a LS-BMD Z-score of -0.5 or worse and have evidence of low impact/fragility fracture at either the Baseline of the Core Study (Group 1) or this study (Group 2).

Group 1: Patients who have received at least one dose of study drug and who have completed the Core study and who meet the inclusion/exclusion criteria for this Extension study will be eligible to enroll. The final visit of the Core study (Visit 8) will serve as the first (screening) visit for the Extension study. At Visit 8A, which may take place on the same day as Visit 8, patients will complete additional screening assessments for the Extension study. Patients will return at Visit 9 (which can also be on the same day as Visit 8 of the Core study) and all patients will receive zoledronic acid. The allowed window for Visit 9 is up to 10 months after Visit 5 (month 6) of the Core study (up to 4 months after Visit 8 of the Core study). Note that Visit 8 and Visit 9 can be combined if the patients or parents or legal guardians have provided informed consent to enter into the Extension study prior to Visit 8 and undergone the appropriate screening procedures as outlined in [Section 6](#). Central labs from Visit 8 will be utilized for the Extension Visit 9, provided the lab samples have been collected within 30 days prior to the Visit 9 infusion. Otherwise, the labs must be redrawn and the results reviewed for eligibility, prior to infusion at Visit 9. The DXA scans (hip, spine and distal femur) from Visit 8 will be used for the extension Visit 9 provided the DXAs have been obtained within 3 months of the Visit 9 infusion; otherwise, the DXA scans must be repeated at Visit 9.

Group 2: Children, male or female, 5 to 17 years of age who otherwise met the inclusion criteria for entry into the Core study but did not complete screening on the Core study because of clinically significant back pain due to vertebral fracture and the preexisting clinical care at the Investigator's site is to treat this type of patient with a bisphosphonate.

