## Statistical methods planned in the protocol and determination of sample size

### Statistical and analytical plans

This document describes the statistical methodology for analyses of efficacy and safety in Study CZOL446H2337E1. The purpose of this study is to extend the period of observation in patients who have completed one year of evaluation in the Core study (CZOL446H2337) to evaluate the long-term safety and efficacy of zoledronic acid in osteoporotic children or adolescents treated with glucocorticoids. To ensure adequate intake of calcium and vitamin D, all children enrolled in this study will be provided with conservative intervention (diet with or without supplements), regardless of their treatment assignment.

The primary objective of this study is to demonstrate that zoledronic acid given long-term, over an additional 12 months from the Core study (CZOL446H2337), is safe for the treatment of osteoporotic children treated with glucocorticoids.

The secondary objectives include:

1. To evaluate the change from core baseline in LS-BMD Z-score at Month 18 and 24 by core treatment group.
2. To evaluate the change from core baseline in LS and total body BMC at Month 18 and 24 by core treatment group.
3. To evaluate the change from core baseline in serum N-terminal propeptide type I collagen (PINP), cross linked N-telopeptide (NTX), bone specific alkaline phosphatase (BSAP) and tartrate-resistant acid phosphatase isoform 5b (TRAP-5b) at Month 18 and 24 by core treatment group.
4. To evaluate the proportion of patients with new clinical vertebral fractures during the 12 month extension period by core treatment group.
5. To evaluate the proportion of patients with new morphometric vertebral fracture during the 12 month extension period by core treatment group.
6. To evaluate the change from core baseline in pain using the Faces Pain Scale-Revised (FPS-R) at Month 15, 18, 21 and 24 by core treatment group.
7. To evaluate the change from core baseline in 2nd metacarpal cortical width at month 24 by core treatment group.
8. To evaluate the change from core baseline in bone age and 2nd metacarpal cortical width at month 24 by core treatment group.

Categorical data will be presented as frequencies and percentages. For continuous data, mean, standard deviation, median, minimum, and maximum will be presented.

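### The objective is change in LS-BMD Z-score, but the Month 18 and 24 ANCOVA analyses percent change in the Z-score, which reverses the sign and weights equal gains by 1/|baseline|

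*SAP*

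**What the plan says.** **Objective.** SAP secondary objective 1 is "To evaluate the change from core baseline in LS-BMD Z-score at Month 18 and 24 by core treatment group". Protocol 2.2, Group 1 objective 1, agrees: "change from baseline 1 (Visit 1 of the Core study) in LS-BMD Z-score at Month 18 and 24".

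**Analysis.** The SAP section Analysis for efficacy variables puts a different variable into the ANCOVA: "The percent change in LS-BMD Z-score at Months 18 and 24 relative to core baseline between zoledronic acid and placebo". The least squares means, treatment difference, 95% CI and p-value are all reported on that scale. Protocol 9.5.1.1 has Change in its heading, but its Group 1 text analyses "the percentage change in LS-BMD Z-score at Months 18 and 24 relative to both baselines between zoledronic acid and placebo". For Group 2 it says "percentage changes in LS-BMD Z-score at Months 18 and 24 relative to Baseline 2 (Visit 8A/9) for zoledronic acid will be evaluated".

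**Definition.** The SAP defines change (Month X value minus baseline) and percentage change as separate variables. For the second: "Percentage change from baseline is defined as 100 times the change from baseline divided by the baseline value". The divisor is the signed baseline, with no absolute value taken.

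**Baseline.** Protocol 3.1: "All patients must manifest a LS-BMD Z-score of -0.5 or worse". For Group 1 this applies at the Core baseline. For this endpoint the SAP says "the efficacy data will be summarized and analyzed with respect to core baseline only", whereas Protocol 9.5.1.1 uses both baselines.

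**Absolute change at Months 18 and 24.** It is covered only by the SAP's general rule for descriptive statistics by core treatment group and visit.

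**The concern.** Percent change suits a quantity with a true zero. A Z-score has none: zero is the reference mean for age and sex, so a ratio to baseline has no natural meaning. Three consequences follow here.

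- With negative baselines, a benefit of zoledronic acid is printed as a negative treatment difference.
- Each child's gain is divided by the size of that child's baseline, so the least affected children dominate the estimate.
- The estimate is not in Z-score units and depends on case mix, so it cannot be read as the change that the objective asks for.

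The Z-score is also the only endpoint treated this way. BMC and metacarpal cortical width are modelled as absolute change, and the bone markers as a log ratio. At stake is the inference for the first-listed efficacy objective.

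**Working it through.** The documents give no effect size, SD or power for this endpoint, so there is no stated figure to reproduce. Steps 1 and 2 need only the SAP definition and the entry limit. Steps 3 to 5 rest on assumptions, which are named.

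**1. Sign and weight.** Percent change = 100 × gain / baseline, with baseline ≤ -0.5. For a gain of +0.5:

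| Baseline Z | Percent change |
|---|---|
| -0.5 | 100 × 0.5 / (-0.5) = -100% |
| -1 | -50% |
| -2 | -25% |
| -4 | -12.5% |

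The same gain counts 100 / 12.5 = 8 times as much at -0.5 as at -4. Read the other way, a constant effect of -25% means +0.125 Z at a baseline of -0.5 and +1.0 Z at -4.

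**2. The ranking of the arms can reverse.** Both arms have baselines -0.5, -1, -2, -4.

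| | Gains | Mean gain | Percent changes | Mean percent |
|---|---|---|---|---|
| Arm A | 0, 0.2, 0.6, 1.2 | 2.0/4 = +0.50 | 0, -20, -30, -30 | -80/4 = -20% |
| Arm B | 0.4, 0.3, 0.3, 0.2 | 1.2/4 = +0.30 | -80, -30, -15, -5 | -130/4 = -32.5% |

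A has the larger mean gain, but percent change puts B ahead. Baselines are identical, so no imbalance is involved. Baseline as an additive covariate does not remove the 1/|baseline| scaling of effect and error.

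**3. Who carries the weight.** Assume baseline is normal with mean mu and SD 1, truncated to -5 to -0.5. A band's weight share is the sum of 1/|Z| in the band over the sum across all patients.

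| mu | Patients in the SAP category -1.0 to -0.5 | Their share of the weight |
|---|---|---|
| -1.5 | 18% | 35% |
| -2 | 10% | 23% |
| -2.5 | 5% | 13% |

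At mu = -2, children at or below -2.0 are 54% of patients and 35% of the weight. A constant true benefit of +0.5 Z gives a mean percent-change estimate of -35%, -29% and -23% at the three values of mu: one effect, three answers.

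**4. Power, for illustration.** Assume a benefit of +0.5, SD of change 0.6, and 15, 25 or 45 per arm. The ANCOVA includes treatment, baseline, condition and region, with 4,000 runs per cell.

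- Constant benefit: percent change loses 5 to 11 points (25 per arm, mu = -2: 77% against 68%).
- Only the benefit scales with |baseline|: it loses 8 to 25 points.
- Benefit and SD both scale: it gains 3 to 7 points (25 per arm: 70% against 77%).

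A separate run with a benefit of 0.4, SD 0.6 and 30, 60 or 100 patients in total gave a loss of about 6 to 11 points under constant benefit.

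**5. Extension baseline (Protocol 9.5.1.1, Group 1 only).** No Z-score limit applies after the Core year. Assume the extension baseline is normal with SD 1 and mean between -1.5 and -0.5. The share of positive denominators is then 1 - Φ(1.5) = 7% to 1 - Φ(0.5) = 31%. The share with |Z| < 0.1 is Φ(1.6) - Φ(1.4) = 3% to Φ(0.6) - Φ(0.4) = 7%. The sign would then differ between patients and some ratios would be extreme. Under the SAP's core-baseline rule this does not arise.

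**The case against.** **Absolute change is reported.** The objective asks to evaluate change by core treatment group and names no test, and the SAP tabulates mean, median, SD and range of change by group and visit. That is correct. What is missing is the adjusted difference, CI and p-value, which the plan supplies for this endpoint only on the percent scale.

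**Other text might cover it.** The SAP's Other analyses lists change in LS-BMD Z-score, and the sample SAS code has a generic change variable. The first covers core visits only and leaves the scale unclear. The second is a template for all ANCOVA endpoints. Neither reaches Months 18 and 24.

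**The sign flip is harmless.** At core baseline it is uniform, so by itself it is a labelling matter and leaves two-sided p-values unchanged. This stands; the weighting is the substantive fault.

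**Reversals are rare.** The example in step 2 is constructed. In a rerun of the three scenarios in step 4 (1,500 runs per cell), the scales disagreed on the better arm in 0.2% to 3.5% of runs at 25 per arm, and were never both significant in opposite directions. They differ on p < 0.05 in 10% to 24% of runs at 25 per arm, but part of that is ordinary crossing of the threshold at moderate power.

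**The assumed inputs have no source.** All extension patients receive zoledronic acid, so Months 18 and 24 compare earlier with later start, and the assumed benefit may be too large. The Z-score limit was also once -1.0, so patients recruited under it cannot fall in the -1.0 to -0.5 band, and the shares in step 3 may overstate that band. Both points stand, and steps 3 and 4 show possible size only.

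**Conclusion.** The concern holds. At Months 18 and 24 the modelled variable is not the one in the objective, and it is a poor scale for a Z-score. The reversed sign and the 8-fold spread in weight between baselines of -0.5 and -4 follow from the SAP definition and the entry limit alone. The possible change in ranking follows from the same definition. The weight shares, power differences and extension-baseline percentages depend on assumed distributions and effects, and percent change does not lose power in every scenario.

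This should be fixed, but its reach is limited: it affects a secondary endpoint in a study whose primary objective is safety, and the data needed are collected and already summarised. Near-zero and positive denominators arise only in the protocol's extension-baseline analysis for Group 1.

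**What to change.** - In the SAP, Analysis for efficacy variables, make absolute change in LS-BMD Z-score (Month X value minus baseline) the ANCOVA response. Keep core baseline Z-score and the other model terms, and report the adjusted difference, 95% CI and p-value in Z-score units.
- Make the same change in Protocol 9.5.1.1 for Group 1, and summarise absolute change for Group 2, which remains descriptive.
- Drop percent change for Z-scores.
- State one rule in both documents for which baseline or baselines this endpoint uses.

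The cost is wording in two places and a change of response variable in one program. The SAP already defines the variable, and no further data or visits are needed.
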